6.3. Patient Enrollment

To minimize selection bias within the enrolled patient population, participation in the study is to be offered to all eligible patients on a consecutive basis as they present to the physician at the site. All eligible patients will be assigned a screening number. The screening log will include minimal health information regarding each non-enrolling patient (e.g., sex, age, reason for not enrolling, etc). As the non-enrolled patients will not sign an informed consent form the data collected will not include personally identifiable information (as defined in 45 CFR 164.514).

Patients who wish to participate in this study and sign a written informed consent form will be assigned a unique identifier number at baseline to be used throughout the study.

CUC10-LNG06-04 Page 10 of 38

6.4. Patient Withdrawal

Patients may withdraw from this study at any time, with or without a reason, without prejudice to further treatment. Investigators should make every effort within the bounds of safety and patient choice to have each patient complete the study. If a patient does not return for a scheduled visit, every effort should be made to contact the patient. In any circumstance, every effort should be made to document patient outcome, if possible. The investigator should inquire about the reason for withdrawal; request the patient return for a final visit, if applicable and follow-up with the patient regarding any unresolved adverse events. As possible, the reason(s) for withdrawal (if given) will be recorded.

If the patient withdraws from the study and also withdraws consent for disclosure of future information, no further evaluations should be performed and no additional data should be collected. The sponsor may retain and continue to use any data collected before such withdrawal of consent.

6.5. Risks

Potential risks of pulmonary tumor cryoablation in the intra operative/early postoperative period include bleeding, cough, hemoptysis, fever, hypertension, pleural effusion, pneumothorax, subcutaneous emphysema and skin injury.

Potential delayed risks of pulmonary tumor cryoablation include pulmonary embolus, acute respiratory distress syndrome and other unforeseen complications.

6.6. Potential Benefits

Cryoablation is an FDA-cleared treatment modality for the ablation of cancerous or malignant tissue and benign tumors, and palliative intervention. Potential benefits of pulmonary tumor cryoablation include palliative relief of symptoms associated with the disease including dyspnea, cough and hemoptysis. Other benefits may include improved lung function and performance status.

6.7. Study Supplies

Study sites will use commercially available device supplies labeled for use specifically for this study. A Regulatory Documents binder will be provided to each site. Questionnaires, patient instructions and applicable worksheets will also be provided to each site. The study monitor should be contacted for any issues related to these study supplies.

Cryoablation needles are supplied in individual single use, sterilized packages. Once opened, they should be used immediately for the current procedure or discarded. Cryoablation needles should be stored according to the recommendations on the commercial packaging.

6.8. Pertinent Concurrent Medications

Data will be collected regarding concurrent pertinent medication taken at the time of screening and through 30 days post procedure. Patients who are taking any contraindicated medications at screening must appropriately wash out before the cryoablation procedure. These medications include, but are not limited to, warfarin (e.g. Coumadin), clopidogrel (e.g. Plavix), Phenindione (e.g. Dindevan) and aspirin. Herbal supplements with blood thinning properties should be washed out of appropriately.

Supplemental treatment which, in the investigator's opinion, becomes necessary during the course of the study must not be denied to the patient. If this supplemental treatment is described as a therapy expressly not permitted the patient's participation in the study may need to be discontinued due to non-permitted concurrent therapy.

CUC10-LNG06-04 Page 11 of 38

7. PATIENT POPULATION

7.1. Patient Selection

This study can fulfill its objectives only if appropriate patients are enrolled. The following eligibility criteria are designed to select patients for whom cryoablation therapy is considered appropriate. All relevant medical and non-medical conditions should be taken into consideration when deciding whether cryoablation therapy is suitable for a particular patient.

7.2. Inclusion Criteria

Eligible patients for this study must meet all of the following criteria:

- 7.2.1. Patient must be at least 18 years old.
- 7.2.2. Patient has signed a written informed consent.
- 7.2.3. Patient presents with Stage 4 pulmonary metastatic disease with metastatic disease previously confirmed by prior biopsy; or
 Patient presents with Stage 4 pulmonary metastatic disease previously confirmed on
 - Patient presents with Stage 4 pulmonary metastatic disease previously confirmed on imaging (e.g. CT or MRI) with known (biopsied) primary disease.
- 7.2.4. Patient has up to 3 local metastases unilaterally targeted by cryoablation. (treatment in both lungs must be on separate treatment days) Maximum number of pulmonary tumors bilaterally per patient will be 5 total pulmonary tumors.
- 7.2.5. Targeted tumor(s) defined as intra pulmonary or pleural with a maximum size of 3.5 cm.
- 7.2.6. The target tumor is determined (by CT/MRI images) to be in a location where cryoablation is technically achievable based on the proximity of adjacent organs and structures.
- 7.2.7. ECOG performance status of 0-2.
- 7.2.8. Karnofsky Performance Scale (KPS) score ≥60.
- 7.2.9. Platelet count >50,000/mm³ within 60 days prior to study treatment.
- 7.2.10. INR < 1.5 within 60 days prior to study treatment.
- 7.2.11. Patient has a life expectancy of >3 months.
- 7.2.12. Patient is clinically suitable for cryoablation procedure.

7.3. Exclusion Criteria

Patients not eligible for participation in this study include patients who have any of the following:

- 7.3.1. Patient's primary cancer is lung cancer.
- 7.3.2. Patient is unable to lie flat or has respiratory distress at rest.
- 7.3.3. Patient has uncontrolled coagulopathy or bleeding disorders.
- 7.3.4. Patient has had chemotherapy with neutropenia to levels (ANC <1000) that produce increase risk for the cryoablation procedure.

- 7.3.5. Patient has a history of an allergic reaction to iodine injections or to shellfish.
- 7.3.6. Patient has evidence of active systemic, pulmonary, or pericardial infection.
- 7.3.7. Patient has a debilitating medical or psychiatric illness that would preclude giving informed consent or receiving optimal treatment or follow up.
- 7.3.8. Patient is currently participating in other experimental studies that could affect the primary endpoint.

CUC10-LNG06-04 Page 12 of 38

8. STUDY PROCEDURES

The study schedule of events and the specific procedures performed at each visit are shown in Table 1, Schedule of Events. Each patient will undergo a total of 11 visits, including an initial/screening visit, the procedure visit, and 9 post-operative visits. The Month 1 post-operative visit may be a telephone visit or a clinic visit. More visits may be required when medically necessary.

Table 1: Schedule of Study Events

Procedures	Screening	Procedure Date	W 1ª	M 1 ^b	M 3, 6 & 12 d	M 24, 36, 48, 60 ^e or Withdrawal
Informed Consent	Х					
Inclusion/Exclusion	Х					
Demographics	Х					
Targeted Medical History	х					
ECOG & Karnofsky	Х		Х	Χ°	Х	Х
Pertinent Medication	Х		Х	Х		
Discontinue anticoagulation, as clinically indicated	х					
CT/MRI Scan ^f	Х		Χg		Х	Х
Record tumor characteristics	х					
Chest X-Ray			Χg			
Cryoablation procedure		Х				
Labs h	Х					
Quality of Life (SF-12) i	Х			X	Х	х
Safety Assessments		Х	Х	Х	Х	Х

^aWeek 1 visit within +/- 7 days of cryoablation procedure

8.1. Screening

The screening period begins after written informed consent has been obtained. The screening visit allows the investigator to assess a patient's eligibility for this study.

CUC10-LNG06-04 Page 13 of 38

b Month 1 visit may be done by telephone interview or clinic visit. Visit window +21/-7 days

Complete only if a Clinic Visit

d Months 3, 6 and 12 visit window +45 days

e Months 24, 36, 48 and 60 visit window +90 days

f CT/MRI scan with contrast for follow-up at 3 months, 6 months, 1 year then yearly per routine post treatment f/u

Week 1 imaging may be a CT, MRI or X-Ray with or without contrast

h Platelet Count, ANC and INR – within 60 days of study procedure

ⁱTo be completed before treatment starts then at 1, 3, 6, 12, 24, 36, 48 and 60 months post cryoablation

The following assessments will be completed during screening and within 6 weeks of the cryoablation procedure:

- Informed consent;
- Review inclusion/exclusion criteria;
- Patient number assigned;
- Demography;
- Targeted medical history, including comorbidities;
- ECOG:
- Karnofsky Performance Scale;
- Baseline labs (Platelet Count, ANC and INR);
- CT/MRI scan of chest with contrast to include lungs, liver, and adrenal glands;
- Tumor characteristics (See Section 5.4);
- Quality of Life assessments (SF-12);
- Current pertinent concomitant medication;
- Discontinue anticoagulation as clinically indicated;
- Assess for clinical safety of General Anesthesia (if applicable).

8.2. Cryoablation Procedure

Galil Medical's Cryoablation System will be used per the manufacturer's guidelines. Galil Medical's cryoablation needles will be placed under CT image guidance in a pattern necessary to fully freeze the target tumor(s). The treatment will be administered utilizing cryoablation needles with compressed argon gas through the Joule-Thomson effect to produce extremely low temperatures within the target tumor(s).

The following data will be collected at the time of the procedure or prior to discharge, as applicable:

- Number of tumors treated with cryoablation
- Tumor size measured by two methods:
 - 3-dimensional measurements (cm) and
 - Greatest trans-axial diameter (cm)
- Number and type of cryoablation needles used
- Number of freeze and thaw cycles
- Freeze and thaw times, per cycle
- Number and type of intra-operative complication(s)
 - Severity of complication(s)
- Requirement for hospital admittance/stay
- Requirement for surgical intervention(s)
- Safety assessments

8.2.1. Cryoablation needle placement

Based upon isotherm data for the cryoablation needles, the distance between adjacent cryoablation needles should be ≤ 15 mm. The number and configuration of the needles will be

CUC10-LNG06-04 Page 14 of 38

based on the necessity to maintain appropriate distances between adjacent cryoablation needles and anatomic structures, and the final number of needles can only be formulated based upon the configuration of the lung tumor at the time of treatment.

The CT imaging views of the lung tumor will enable final assessment of the percutaneous access route and needle placement on the day of the procedure. Cryoablation needles will be placed to create multiple overlapping iceballs to completely cover the tumor and provide a 5 mm zone of ablation surrounding the tumor while maintaining appropriate safe distance from the non-targeted tissues (i.e. main bronchus and pulmonary arteries).

8.2.2. Cryoablation needle testing

Before anesthesia inducement of the patient, all cryoablation needles should be tested in accordance with Galil Medical's Cryoablation System User Manual to confirm their freezing function and structural integrity.

8.2.3. Freezing procedure

Once freezing has been initiated, the cryoablation procedure may be monitored with non-contrast CT imaging at 2-5 minutes intervals to visualize iceball growth, to ensure the ablation zone is adequately frozen and adjacent anatomical structures are protected. As the freezing continues, the ice formation from each of the cryoablation needles coalesce so the targeted portions of the ablation zone are frozen. The ablation zone should be monitored continuously under CT imaging guidance during the procedure. When the leading edge of the ice has reached at least 5 mm beyond the tumor periphery, the freezing process should be stopped. Typically, three freeze-thaw cycles should be utilized. Passive or active thaw should be carried out with at least a 5 minute thaw between freeze cycles. Following the last freeze cycle, a brief (up to 10 minute) active thaw should be utilized prior to attempting to remove the needle(s). Passive thawing will complete the melting of the ice. A technically successful treatment will be defined as an ablative margin of at least 5 mm beyond the edge of the tumor.

8.2.4. Procedure completion

CT images are typically obtained in the transverse and longitudinal planes showing the greatest extent of freeze. On the transverse view, the medial extent of the ice should encompass all treated tissue at least 5 mm beyond the tumor periphery. After cryoablation needle removal, CT images will be obtained to assess any bleeding or pneumothorax development. If a pneumothorax is diagnosed it should be managed per standard of care.

If intrapulmonary, endobronchial, or intrapleural bleeding occurs, a clinical assessment will determine whether transfusion is necessary and subsequent CT imaging will determine whether the bleeding is increasing over time. If the bleeding continues to increase over time, it will be managed per standard of care.

An antibiotic of choice can be prescribed to prevent post-operative infection.

8.3. Week 1 - Follow-up

Within 1 Week (+/- 7 days) post cryoablation procedure patients are to complete the following assessment:

- ECOG:
- Karnofsky Performance Scale;
- Chest x-ray or CT/MRI, with or without contrast;

CUC10-LNG06-04 Page 15 of 38

- Safety assessments;
- Surgical intervention(s), as applicable;
- Current pertinent concomitant medication.

8.4. Month 1 - Follow-up (Telephone Interview or Clinic Visit)

Patients may be contacted by telephone or return 1 Month (+21/-7 days) post cryoablation procedure to complete the following assessments:

- Quality of Life assessments (SF-12);
- ECOG (Clinic Visit Only);
- Karnofsky Performance Scale (Clinic Visit Only);
- Safety assessments;
- Assess any new cancer treatment(s);
- Current pertinent concomitant medication.

8.5. Months 3, 6 and 12 - Follow-up

Patients will return 3, 6 and 12 Months (+/-45 days) post cryoablation procedure to complete the following assessments:

- ECOG:
- Karnofsky Performance Scale;
- Quality of Life assessments (SF-12);
- CT/MRI Scan, with contrast;
- Safety assessments;
- Assessment of disease progression, including retreatment;
- Assess any new cancer treatment(s).

8.6. Months 24, 36, 48, 60 and Study Completion or Withdrawal

Patients will return 24, 36, 48 and 60 months (+/- 90 days) post cryoablation procedure or at Study Withdrawal and complete the following assessments:

- ECOG;
- Karnofsky Performance Scale;
- Quality of Life assessments (SF-12);
- CT/MRI Scan, with contrast:
- Safety assessments;
- Assessment of disease progression, including retreatment;
- Assess any new cancer treatment(s).

Patients who request Early Termination from the study will be asked to return for a final visit to complete the above assessments.

Patients may be considered "lost to follow-up" after 3 unsuccessful attempts to contact the patient with on contact being a registered letter to the last known address of the patient. Site should document all attempts to contact the patient in the source documents.

CUC10-LNG06-04 Page 16 of 38

9. ASSESSMENTS

9.1. Demography

Demographic information will be collected from the patient during screening. The information will consist of date of birth, race and sex.

9.2. Targeted Medical History

Targeted medical history information must be obtained from each patient entering the study. Obtaining accurate medical history is necessary to ensure documented baseline health status and to ensure that patients meet study entry criteria.

9.3. Laboratory Tests

Laboratory tests will be performed by the site's local laboratory. The following laboratory tests are required within 6 weeks of the cryoablation procedure.

- Platelet Count;
- ANC;
- INR.

9.3.1. Biopsy

A biopsy of a tumor(s) in the lung(s) metastasized from another primary disease may be obtained at the discretion of the treating investigator per his/her standard practice.

9.4. Physical Performance

Physical function assessments will be measured using Eastern Cooperative Oncology Group (ECOG) and Karnofsky Performance Scale (KPS).

Performance Status - ECOG

A set of criteria with corresponding scores used by the investigator to assess how a patient's disease is progressing, assess how the disease affects the daily living abilities of the patient, and determine appropriate treatment and prognosis. (See Appendix C)

ECOG will be assessed at screening, Week 1 and Months 3, 6, 12, 24, 36, 48 and 60.

Karnofsky Performance Scale (KPS)

The Karnofsky Performance Scale is a standard way of measuring the ability of cancer patients to perform ordinary tasks. The scores range from 0 to 100. A higher score means the patient is better able to carry out daily activities. KPS may be used to determine a patient's prognosis, to measure changes in a patient's ability to function. (See Appendix D)

KPS will be assessed at screening, Week 1 and Months 3, 6, 12, 24, 36, 48 and 60.

9.5. Quality of Life

To measure quality of life this study will use the Short Form (SF)-12 generic measure.

SF-12 will be completed by the patient at screening, Months 1, 3, 6, 12, 24, 36, 48 and 60. (See Appendix E)

Short Form - 12 (SF-12)

The SF-12 is a shortened version of the well-known SF-36. The SF-12 assesses eight domains (physical functioning, role limitations due to physical health problems, bodily pain, social

CUC10-LNG06-04 Page 17 of 38

functioning, general mental health, role limitations due to emotional problems, vitality and general health perception).

9.6. Computed Tomography (CT) and Magnetic Resonance Imaging (MRI)

As outlined in this protocol, all patients will have an initial CT or MRI prior to therapy. The cryoablation procedure will be completed under CT guidance only. Follow-up imaging at Week 1 will be either CT, MRI or X-Ray. At Months 3, 6, 12, 24, 36, 48 and 60, follow up imaging will be CT or MRI with contrast unless contrast is contraindicated.

9.7. Response Determination

The tumor(s) treated will be defined as the target tumor. The baseline size(s) will be measured on the pretreatment CT/MRI scan.

Local tumor control will be defined as follows:

9.7.1. Local Control

Local control will be defined as the absence of local failure.

9.7.2. Complete Response

Tumor disappearance (scar) or <25% of original size.

Note: If it is the opinion of the investigator that the tumor has likely disappeared, the measurement should be recorded as 0mm. If the tumor is believed to be present and is faintly seen but too small to measure, a default value of 5mm will be assigned.

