9.7.5. Local Failure

Local failure will be defined as >20% increase in the sum of the largest diameter of all targeted tumors.

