#### **Analysis Methods**

Patients may have up to five tumors so tumor control will be calculated on a per tumor level as well as a patient level. To be considered a success on a patient level all tumors treated during the baseline procedure must meet the tumor control criteria at that follow-up visit.

Post-treatment imaging including CT/MRI will be reported for baseline and follow-up visits. Tumor control for each time point will be determined by examining the change from baseline, and will be defined as:

Complete Response – Tumor disappearance or a  $\geq$  75% decrease in the greatest transaxial diameter ( <25% of original size).

Partial Response – A <75% but ≥30% decrease in the greatest trans-axial diameter.

**Stable Disease** – No change, allowing for a <30% decrease up to a <20% increase in the greatest trans-axial diameter.

**Local Failure** – A ≥20% increase in the greatest trans-axial diameter.

**Local Control** – Local control will be defined as the absence of local failure. Tumors in complete response, partial response and stable disease will all be in local control.

**Distant Failure** – Distant failure (e.g. metastatic disease) will be defined as the appearance of distant cancer deposits consistent with metastatic spread of cancer outside the intended treatment area.

The local tumor control counts and rates will be presented along with the 95% two-sided confidence intervals for the rates. The rate at the each visit will be defined as the proportion of tumors/patients experiencing tumor control at a specific time point out of the number of patients who complete a follow-up visit at that time point.

Efficacy analyses will be performed on the ITT population. Analysis of the PP population may be done in support of the ITT analysis. No formal statistical hypothesis testing will be performed for efficacy endpoints.

Confidential Page 3 of 9

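### A fixed 5 mm default codes an unmeasurable remnant as local failure when baseline was below 4.17 mm; cap it at baseline, and examine reading noise in small tumors by sensitivity analysis

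*Protocol*

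**What the plan says.** Protocol 9.7.2 gives two recording rules for follow-up imaging. If the investigator believes that "the tumor has likely disappeared, the measurement should be recorded as 0mm". If a tumor is still present but "faintly seen but too small to measure, a default value of 5mm will be assigned". The second rule does not depend on how large the tumor was at baseline. It does not say whether it also covers the baseline reading, and the SAP does not repeat it.

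Protocol 7.2.5 defines the target as "intra pulmonary or pleural with a maximum size of 3.5 cm". There is no minimum.

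Local failure is relative in both documents, but the two definitions differ. Protocol 9.7.5: "Local failure will be defined as >20% increase in the sum of the largest diameter of all targeted tumors". SAP, Efficacy Endpoint Analysis, Analysis Methods: "A ≥20% increase in the greatest trans-axial diameter". Neither adds a minimum increase in millimetres, a minimum measurable baseline or a confirmatory reading. The reference is the pretreatment size: "Tumor control for each time point will be determined by examining the change from baseline".

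Local control is the absence of local failure (Protocol 9.7.1 and SAP). A patient counts as a success only if every treated tumor is controlled at that visit (Protocol 11.5.2 and SAP).

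For complete response the protocol has "Tumor disappearance (scar) or <25% of original size". The SAP asks for a decrease of 75% or more and adds, in brackets, less than 25% of the original size.

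**The concern.** A fixed imputed value judged by a percentage can run the wrong way. If the baseline is smaller than the imputed value, a tumor that has faded below measurability is recorded as having grown. Local control is the only efficacy endpoint, and one failing tumor fails the patient under the SAP's rule, so the miscoding goes straight into the main result.

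The same purely relative limit leaves little room for reading error in small tumors. The trial tests no hypothesis, but both documents say that its estimates will be used to power a pivotal study. False failures would lower the control rate carried forward, by an amount that depends on the size mix enrolled.

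**Working it through.** The documents give no derived figure to reproduce. The check applies their own thresholds.

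**Inputs.** From the documents: default 5 mm (Protocol 9.7.2); maximum 35 mm, no minimum (7.2.5); failure at more than 20% of the summed diameters (9.7.5) or at 20% or more of a tumor's trans-axial diameter (SAP); 30 to 40 patients. Assumed, because the documents give no reading error: single-reading SD *s* from 0.5 to 2 mm, with normal, independent errors.

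**1. The default.** Recorded change is 5/b − 1 for baseline b. It reaches +20% at b = 5/1.2 = 4.17 mm.

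| Baseline (mm) | Change at default | Coded as (SAP) |
|---|---|---|
| 4.0 | +25.0% | local failure |
| 4.1 | +22.0% | local failure |
| 4.2 | +19.0% | controlled |
| 5 | 0% | controlled |
| 10 | −50.0% | controlled |
| 20 | −75.0% | controlled |

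From 4.2 mm upward the default never produces a failure. Under the protocol's sum rule a lone 4 mm tumor also fails. Beside an unchanged 5 mm tumor, however, the sum goes from 9 to 10 mm (+11.1%) and does not fail.

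**2. The complete-response cut.** At b = 20 mm the default gives 5/20 = 25% of baseline, a decrease of exactly 75%. That meets the SAP's decrease criterion but not its bracketed one. The SAP's partial response stops short of 75%, so on the bracketed reading the tumor has no category.

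**3. The 20% limit in millimetres, 0.20 × b.** It is 1 mm at 5 mm, 2 mm at 10 mm, 4 mm at 20 mm and 7 mm at 35 mm. A difference of 1 to 2 mm can therefore decide failure for baselines up to about 10 mm. At exactly +20% (5 to 6 mm, 10 to 12 mm) the SAP records a failure and the protocol does not.

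**4. False failure with no true change, SAP per-tumor rule.** The difference of two readings has SD s√2, so P = 1 − Φ(0.20b/(s√2)).

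| Baseline | s = 0.5 mm | s = 1 mm | s = 2 mm |
|---|---|---|---|
| 5 mm | 7.9% | 24.0% | 36.2% |
| 10 mm | 0.2% | 7.9% | 24.0% |
| 20 mm | 0.0% | 0.2% | 7.9% |
| 35 mm | 0.0% | 0.0% | 0.7% |

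**5. The same under the protocol's sum rule.** With one tumor it is the same calculation. With three unchanged 10 mm tumors the limit is 0.20 × 30 = 6 mm and the SD of the summed difference is s√6, so P = 1 − Φ(6/(s√6)). The per-tumor rule gives 1 − (1 − p)³, with p from step 4.

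| Three 10 mm tumors | s = 0.5 mm | s = 1 mm | s = 2 mm |
|---|---|---|---|
| SAP per-tumor rule | 0.7% | 21.8% | 56.1% |
| Protocol sum rule | <0.001% | 0.7% | 11.0% |

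**6. Weight of one patient.** 1/30 = 3.3 points; 1/40 = 2.5 points. As an illustration with exact intervals, 30/30 (95% CI 88.4% to 100%) becomes 29/30 (82.8% to 99.9%).

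**7. Capping the default at baseline.** Change becomes min(5, b)/b − 1. This is 0% for every b below 5 mm and as now from 5 mm upward. The only single-tumor outcomes that change are those at or below 4.17 mm, from failure to stable.

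**8. A 5 mm absolute floor in the definition (illustration).** The limit becomes max(0.20b, 5 mm). At 10 mm the false-failure probability falls from 7.9% to 0.02% (s = 1 mm) and from 24.0% to 3.9% (s = 2 mm). But 0.20b reaches 5 mm only at b = 25 mm, so the limit rises for every smaller tumor: a 5 mm tumor would have to double, and a 10 mm tumor grow by 50%, before failing.

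**The case against.** The strongest reply is that the default does harm only when a tumor was measured at baseline at less than the value later assigned to tumors too small to measure. Nothing shows that such tumors will be treated. If the default also governs the baseline reading, 5 mm to 5 mm is no change. This stands as a limit on frequency, but the text does not exclude the case or settle the baseline question.

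A reader might also infer that, because the same finding is stable disease at 5 to 7 mm, partial response at 8 to 19 mm and complete response above 20 mm, baseline size drives the efficacy endpoint. The documents do not support that: the SAP counts all three categories as local control. The shifts affect only the descriptive response summary.

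Nor can one say without qualification that patients with several small tumors are penalised most. That holds under the SAP's per-tumor rule; under the protocol's sum rule the errors partly cancel (step 5).

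Finally, the reading SD is assumed, the baseline size distribution is unknown, and the study is descriptive. So the noise figures show what could happen and are not estimates for this trial. That argues against changing the main failure definition on their strength. It does not argue against examining the effect, since the control rate feeds a pivotal design.

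**Conclusion.** The point holds in a limited form. As written, an unmeasurable remnant is a local failure whenever the recorded baseline is below 4.17 mm. This follows from the documents' own numbers and needs no assumption beyond the default not being applied at baseline. It is an edge case of unknown frequency; each occurrence would move the patient-level rate by 2.5 to 3.3 points with 30 to 40 evaluable patients, and by more at visits with fewer.

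Reading noise is a second, conditional issue, largely confined to small tumors: about 0.2% to 24% per visit for an unchanged 10 mm tumor under the SAP's rule, across the assumed SD range. The width of that range is itself a reason not to build a correction into the main definition.

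A reader might conclude that a 5 mm minimum increase belongs in that definition, because 5 mm is the protocol's limit of measurability. The protocol gives 5 mm as a value to impute, not as a measurement limit or a smallest detectable change. A floor at that level would also loosen the criterion for all tumors below 25 mm, when the reference is already baseline rather than the smallest earlier value.

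**What to change.** 1. In Protocol 9.7.2, set the default to the smaller of 5 mm and that tumor's baseline diameter, and state whether the default can apply to the baseline reading. Carry the rule into the SAP's efficacy methods. Cost: a sentence in each document. No tumor with a baseline of 4.2 mm or more changes its local-control status under the per-tumor rule.

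2. Keep one complete-response cut in both documents, for instance a decrease of 75% or more, and delete the other expression. Cost: wording only; local control is unaffected.

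3. Add to the SAP a sensitivity analysis of local control in which failure requires both the 20% increase and an absolute increase, with the margin chosen and justified by the sponsor in advance. Leave the main definition relative. Cost: one extra table per visit from data already collected. It will call some true growth in small tumors later, and imaging is yearly after month 12, so it should be read beside the main result and not replace it.

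4. State which failure rule applies at tumor and patient level, since the protocol's sum rule and the SAP's per-tumor rule give different answers both here and at exactly +20%.
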